## **RESEARCH DESIGN AND METHODS**

This is an interventional study where up to 60 subjects with active and untreated P-HPTH will be evenly randomized to receive eplerenone, amiloride or placebo in a double-blinded fashion. It is anticipated that up to 75 subjects will need to be enrolled to account for participant non-completion and withdrawals. After 4 weeks +/- 3 days of treatment, each study arm will receive cinacalcet in addition to their blinded experimental therapy. There are 3 main study visits as well as additional safety visits, which are described below. All visits will occur in the outpatient clinical research centers at BWH.

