## **SAMPLE SIZE:**

A sample size of up to 60 total subjects has been chosen using very conservative calculations stemming from our preliminary data (see Detailed Protocol). Therefore, at most there will be 20 subjects per study arm; however, our sample size calculations suggest that we are likely to be adequately powered with a significantly smaller sample size as well. These sample size calculations to achieve sufficient power to observe the primary and secondary outcomes of the study:

- **Primary Outcome:** Change in PTH levels ( $\Delta$ PTH) following randomized drug intervention (**Figure; visits A=>B**).
- **Secondary Outcomes:** Change in serum iCa and markers of bone resorption following randomized drug intervention (**Figure; visits A=>B**).
- Exploratory Outcome 1:  $\Delta$ PTH in response to amiloride therapy (**Figure; visits A=>B**)
- Exploratory Outcome 2:  $\Delta$ PTH in response to combination drug therapy with EPL+ cinacalcet (**Figure; visits A=>B**).
- Exploratory Outcome 3: Correlation of eplerenone-induced  $\Delta$ PTH with MR expression from adenomatous/ hyperplastic parathyroid glands of subjects that undergo parathyroidectomy following study completion.

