  - **Visit C:** 2 weeks +/- 3 days later to assess study outcomes following cinacalcet add-on therapy. Additional safety visits are involved (black diamonds in **Figure**).

- **Study Drug Interventions:** Enrolled subjects will undergo detailed measurements of outcome variables (see detailed outcome variables below) to establish a baseline (**Figure, visit A**). All study visits will be conducted in the morning, following at least 1 hour of monitored supine rest in the Clinical Research Center. Following study visit A, subjects will be randomized to the blinded study drug by the BWH Research Pharmacies. The initial dose of the blinded study drug will be dictated by the subject's blood pressure and the PI's clinical judgment as it relates to reasonable safety. Subjects with blood pressures near the lower range of our safety margin of 105/50 mmHg will receive the lowest dose, and subjects with higher blood pressures (or known hypertension) will receive a higher dose. The initial doses will range from: eplerenone (EPL) 12.5 mg/d to 25 mg/BID, amiloride 1.25 mg/d to 2.5 mg/BID, or placebo. The EPL arm represents the active intervention: a direct MR antagonist. The placebo arm represents a negative control. Since EPL is expected to influence more than just PTH (EPL will also decrease blood pressure and urinary excretion of potassium and calcium) when compared to placebo, the amiloride intervention represents a *second control* to provide insights into the *mechanism* by which EPL may influence PTH. Like EPL, amiloride is a potassium-sparing diuretic, with mild anti-hypertensive and hypocalciuric effects, and will therefore induce similar changes in blood pressure and urinary potassium/calcium excretion. Unlike EPL, amiloride does not directly block the MR. Rather, it blocks epithelial sodium transport channels (ENaC) in the renal distal tubule (and vascular epithelium).

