- *Outcome assessment:* The following measurements will be obtained while fasting at every study visit (**A, B, C**): serum PTH, iCa and total serum calcium, serum phosphate and fibroblast growth factor-23 (FGF-23), 25(OH)D, markers of bone resorption (serum C-telopeptide, urinary N-telopeptide, tartrate-resistant acid phosphatase 5b), markers of bone formation (osteocalcin, bone-specific alkaline phosphatase, P1NP), basic metabolic panel with creatinine, plasma renin activity, serum angiotensin II and ALDO. In addition, 24h urine collections at every study visit, as described above, will be used to measure urinary sodium, potassium, calcium, magnesium, and aldosterone.

Measures of PTH and calcium will be obtained in a standardized fashion after at least 1h of supine rest, at 1h of supine rest, 2h of supine rest, and 3h of supine rest. Subjects will have the option of receiving separate venipunctures at each hour or having an IV placed in their arm for the duration of the study visit which will be used to draw aliquots every hour. The lowest PTH value will be used in analyses.

At study visit A, peripheral blood will be collected for DNA isolation. Although no genetic studies are planned at this time, this DNA will be stored to test future research hypotheses.

Parathyroid tissue will be collected from any subjects that undergo parathyroidectomy (for clinical indications determined by their providers) in the 5 years following their study completion. It is estimated that ~50% of participating subjects may have a surgical parathyroidectomy in the 5 years following their study completion. If the surgery occurs at BWH or MGH, tissue will be collected and flash frozen in liquid nitrogen in the operating room and stored in the BWH pathology

repository, and also formalin fixed in paraffin. Samples will be analyzed for mRNA and protein expression of MR to determine whether there is a correlation of eplerenone-induced  $\Delta$ PTH with MR expression from adenomatous/ hyperplastic parathyroid glands of subjects that undergo parathyroidectomy following study completion. If the surgery occurs at a non-Partners institution, formalin fixed paraffin embedded blocks of tissue will be requested to core a sample and return the block.

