## Statistical Plan

**Analytic Plan, Sample Size and Power:** A sample size of 20 subjects per intervention arm (n=60 total) has been chosen using conservative calculations. The **primary outcome**,  $\Delta$ PTH in response to randomized drug therapy, will be analyzed using a 2-arm ANOVA analysis evaluating the difference between EPL and placebo. A 3-arm ANOVA including the amiloride arm will also be conducted. Sample size calculations are presented in **Figure** using preliminary data from the RAAS-PARC study where the  $\Delta$ PTH= -13 pg/mL was seen with RAAS inhibition in participants with P-HPTH, but also using a more conservative estimate (-9.0 pg/mL) that is 25% lower. It is expected that  $\Delta$ PTH with placebo will range from 0 to +4.57 pg/mL, and calculations have been made to anticipate that amiloride may serve as either a negative control (like placebo) or positive control (like EPL). With these conservative estimates, a sample size of 20 subjects/arm will be sufficient to demonstrate a  $\Delta$ PTH with a type I error of <0.05 and power=80%.

The **secondary outcomes**, change in calcium, will be analyzed in the same fashion as PTH. For calcium, sample size calculations are based on decreases in *total calcium* seen in the RAAS-PARC study ( $\Delta$ Ca= -0.32 mg/dL); treatment with EPL is expected to result in a much greater effect estimate. Thus, using *conservative* estimates of  $\Delta$ Ca= -0.20 to -0.32 mg/dL, a sample size of 20 subjects per intervention arm will be sufficient to achieve 80% power.

**Figure:** Sample size calculations based on  $\Delta$ PTH.

	$\Delta$ PTH	$\Delta$ PTH	$\Delta$ PTH	SD	Sample Size per Arm	
	Placebo	Amiloride	SPIRO		PWR=0.8	PWR=0.9
2-arms	0 pg/mL	-	-9.0 pg/mL	9.4	19	24
	0 pg/mL	-	-13.0 pg/mL	9.4	10	13
	0 pg/mL	0 pg/mL	-9.0 pg/mL	9.4	17	22
	0 pg/mL	0 pg/mL	-13.0 pg/mL	9.4	9	11
	0 pg/mL	-6.5 pg/mL	-13.0 pg/mL	9.4	12	15
	0 pg/mL	-9.0 pg/mL	-13.0 pg/mL	9.4	11	14
3-arms	0 pg/mL	-13.0 pg/mL	-13.0 pg/mL	9.4	9	11

**Figure:** Sample size calculation based on  $\Delta$ Ca.

	$\Delta$ Ca	$\Delta$ Ca	$\Delta$ Ca	SD	Sample Size per Arm	
	Placebo	Amiloride	SPIRO		PWR=0.8	PWR=0.9
	0 mg/dL	0 mg/dL	-0.20 mg/dL	0.21	17	22
	0 mg/dL	0 mg/dL	-0.32 mg/dL	0.21	8	10

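### Exploratory Outcome 3, as worded, correlates gland MR expression with PTH change in eplerenone subjects only, so the tissue analysis cannot separate modification of the drug effect from an association present in every arm

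*Protocol*

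**What the plan says.** The protocol's Sample Size section gives the third exploratory outcome as "Exploratory Outcome 3: Correlation of eplerenone-induced" change in PTH with MR expression in glands from subjects who have a parathyroidectomy after the study. The outcome assessment text under Study Procedures repeats it: "Samples will be analyzed for mRNA and protein expression of MR to determine whether there is a correlation of eplerenone-induced" change in PTH.

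The tissue itself is not restricted by arm: "Parathyroid tissue will be collected from any subjects that undergo parathyroidectomy" for clinical reasons within 5 years of completing the study. On yield, the protocol says: "It is estimated that ~50% of participating subjects may have a surgical parathyroidectomy in the 5 years following their study completion". Subjects are "evenly randomized to receive eplerenone, amiloride or placebo in a double-blinded fashion", and "at most there will be 20 subjects per study arm".

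The protocol describes the amiloride arm as a second control, there "to provide insights into the *mechanism* by which EPL may influence PTH". Neither statement of Exploratory Outcome 3 mentions a correlation in the placebo or amiloride arms, or a comparison of arms. The SAP text available covers change in PTH and in calcium and gives no method for this outcome.

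**The concern.** No subject's eplerenone-induced change is observed. What is observed is the change from visit A to visit B, which also contains drift, measurement variation and regression to the mean. Subjects enter on raised calcium, raised PTH or both, and the PTH analysed is the lowest of several hourly values. If MR expression is related to gland size, baseline PTH or PTH variability, it can track the change in PTH on any treatment, including placebo.

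A correlation within EPL therefore answers whether expression goes with PTH change among treated subjects. The mechanistic question is whether expression changes the effect of eplerenone, and that needs the same relation in a control arm for comparison. Among the listed outcomes this is the only one that looks at MR in the gland itself. A positive EPL-only result could easily be taken as support for MR mediation when no treatment-by-expression effect exists.

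**Working it through.** **The plan's own figures.** The documents give no sample size for this outcome. The primary one reproduces. For a difference of 9.0 pg/mL and SD 9.4, at two-sided 0.05 (sidedness is not stated) and 80% power, the normal formula gives n = 2 × (1.960 + 0.842)² × 9.4² / 9.0² = 17.1, so 18 per arm. The t-test calculation gives 18.1, so 19, as the SAP states. Nothing below disturbs that figure.

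**Inputs for the tissue analysis.**
- At most 20 subjects per arm (protocol, Sample Size).
- About 50% may have surgery within 5 years (protocol, Study Procedures).
- Assumed: the same yield in each arm, hence 20 × 0.5 = 10 tissues per arm and 30 in all.
- Assumed: two-sided 0.05, and 80% as the power benchmark. The SAP sizes the primary outcome "with a type I error of <0.05 and power=80" per cent and sets nothing for this outcome.

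**Step 1: what the EPL-only correlation can show.** On the Fisher z scale its standard error is 1/√(10 − 3) = 0.378.
- Detectable correlation at 80% power: tanh(2.802 × 0.378) = tanh(1.059) = 0.79.
- 95% interval for an observed r of 0.5: tanh(0.549 ± 1.96 × 0.378), which is −0.19 to 0.86.

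**Step 2: how often it is significant with no MR-specific effect.** Let expression have the same correlation with PTH change in every arm, so that it modifies nothing. The common values are assumptions; the documents give none. Simulated rejection rates for a Pearson test with n = 10:

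| Common correlation in every arm | EPL-only test significant |
|---|---|
| 0.3 | about 13% |
| 0.5 | about 33% |

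The Fisher approximation gives 13% and 31%. In the same setting, the EPL-minus-placebo slope difference from a three-arm regression with separate slopes rejects in about 5% of simulated trials at either value.

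**Step 3: precision of the comparison that is missing.** The standard error of a difference between two independent correlations on the z scale is √(1/(n₁ − 3) + 1/(n₂ − 3)). With a control correlation of 0, power is Φ(atanh(r)/SE − 1.96), and the EPL correlation needed for 80% power is tanh(2.802 × SE).

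| Comparison | SE | Power, r = 0.5 vs 0 | EPL r needed for 80% power |
|---|---|---|---|
| EPL vs placebo (10 vs 10) | √(1/7 + 1/7) = 0.535 | Φ(0.549/0.535 − 1.96) = 18% | 0.90 |
| EPL vs pooled controls (10 vs 20) | √(1/7 + 1/17) = 0.449 | Φ(0.549/0.449 − 1.96) = 23% | 0.85 |

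If the yield differs from 50%, the correlation needed against pooled controls is 0.95 at 30% yield, 0.77 at 70% and 0.68 at 100%. These figures stand in for slope differences and assume similar spread of expression and of PTH change in each arm.

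**The case against.** The strongest reply is that the restriction to EPL is inferred from one adjective. The protocol does not rule out a control-arm analysis, names no test, and assays samples from any subject who has surgery, which would permit a comparison across arms. The Detailed Protocol to which it refers, and part of the SAP, were not available. This stands in part: a reader might infer that the sponsor has deliberately excluded the control arms, and the documents do not support that. But both statements of the outcome describe a quantity that can exist only in EPL subjects, and no available text names a comparator.

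A reader might also infer that the 13% to 33% in Step 2 is a false positive rate to be set against a nominal 5%. It is not. The null hypothesis of a correlation test is zero correlation; when the true value is 0.3 or 0.5, rejecting is correct, and these figures are power. The error arises only if the result is then presented as evidence of an MR-dependent drug effect.

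A third tempting reading is that the trial cannot address MR specificity at all. The protocol assigns that question to the randomised comparison of EPL with placebo and amiloride, and this point leaves that comparison intact.

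Finally, the added comparison will seldom settle the matter. That is true, as Step 3 shows: 30 tissues do not make the EPL-placebo contrast larger than 10 against 10. It is a reason to report an estimate with its interval. It does not make the EPL-only correlation an answer to the mechanistic question.

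**Conclusion.** The concern holds, limited to the tissue analysis. As worded, Exploratory Outcome 3 cannot separate modification of the eplerenone effect by MR expression from an association common to all arms, although tissue that would allow the comparison is already to be collected and assayed. The primary and secondary analyses and the sample size are unaffected. The importance is low, since this is one exploratory outcome on incidental tissue.

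The sizes rest on four assumptions: 20 completers per arm, about 50% yield in each arm, a two-sided 0.05 level, and, for the 13% to 33%, a common correlation of 0.3 to 0.5. The protocol's 50% is worded as what may happen, and flash-frozen tissue is promised only for surgery at the two named hospitals, so 10 per arm may be optimistic. Surgery also takes place after randomisation. If the decision to operate depends on response, randomisation does not fully protect the comparison among subjects with tissue, which is a further reason to keep it exploratory.

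**What to change.** Keep the within-EPL correlation as a description. Add to the SAP a regression of change in PTH from visit A to visit B on arm, MR expression and arm-by-expression, using tissue from all three arms. Report the EPL-minus-placebo and EPL-minus-amiloride differences in slope with 95% confidence intervals, labelled exploratory, and base any statement about MR-dependent response on those differences and not on the EPL correlation alone.

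State the expected precision beside the analysis: about 18% power (vs placebo) or 23% (vs pooled controls) to separate a correlation of 0.5 from 0 with about 10 tissues per arm, and 80% power only for an EPL correlation of about 0.85 to 0.90. Give the number of tissues obtained in each arm. Before making the change, the sponsor should check whether the Detailed Protocol already specifies a control-arm comparison.

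The cost is a few lines of SAP text. No new subjects, samples or assays are needed, and the text should be fixed before expression and PTH data are analysed together.

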### **STUDY PROCEDURES:**

- ***Screening Visit:*** Subjects will be contacted via telephone or Doximity Dialer to confirm eligibility and schedule screenings visits. Doximity Dialer will be used to minimize in-person contact if study staff are unable to go into research facilities due to the COVID-19 pandemic. An in-person screening visit will involve a physical examination, blood pressure measurement, detailed history intake by the study PI, and if needed, screening labs to determine eligibility. Subjects who have had the necessary screening laboratories for clinical purposes in the 6 weeks preceding this screening visit (including serum calcium, PTH, potassium, creatinine, HbA1c) will not be required to repeat this testing if it is available for the PI to verify. Pregnancy testing for women aged 18-50 will be a part of the screening visit, as well as Study Visits 1, 3 and 5. Menopausal women who have not had a period for the past 12 months or more, will not need to have a pregnancy test. Also, participants who have had any well-documented method of surgical sterilization will not need to have a pregnancy test. Methods of surgical sterilization include having had a hysterectomy, bilateral oophorectomy, a tubal ligation, or transvaginal occlusion. All other female participants must have a negative pregnancy test before starting the study drug.

Females who are sexually active and able to become pregnant, must agree to use an approved method of birth control for the entire study and for at least 1 month after their last dose of study drug. Abstinence, condoms, diaphragms, birth control pills, birth control patches and birth control injections will be considered acceptable methods. If the participant plans to use a birth control pill, patch or injection, they will be instructed to start using it at least one month before the washout period.

The screening visit will also provide time for the PI to describe the study procedures and risks in detail, review the consent form (which the subject will have had for >24 hrs prior to the visit), and provide informed consent.

[figure not shown]
In light of the COVID-19 pandemic, a remote screening visit procedure has been developed to minimize in-person contact if potential participants and study staff are unable to go into research facilities. This visit will be done by phone and televisit. We will schedule a time to complete the first portion of the screening visit over the phone at a time that is most convenient for the participant. The first portion of this visit will entail at-home monitoring of blood pressure. We will provide an at-home blood pressure monitor for the participant to measure blood pressure. Participants will be asked to remain seated with feet flat on the ground and to rest for 5-minutes prior to beginning these measurements. After 5-minutes, participants will be instructed to measure and record blood pressure and pulse three times, 2-minutes apart. At the time of the scheduled phone call, these blood pressure measurements and current height and weight are to be reported to us. In addition, personal medical history will be reviewed. If the participant meets the preliminary requirements of the study, a televisit will be scheduled with the study investigator/physician for further evaluation of eligibility.

Participants will then undergo a brief physical examination and confirmatory review of past medical history via televisit with the study investigator/physician. If the remote screening visit shows result consistent with inclusion criteria, and does not meet any exclusion criteria, we will inform the participant of their eligibility to come in for screening labs. This entails a blood draw and a urine pregnancy test (if applicable), to ensure there are no abnormalities that would

prevent participation. If the results of the screening labs meet the requirements of the study, we will inform participants within a few days that they are eligible to participate.

If participants are unable to physically come in to have screening labs drawn, they will be asked to inform us. Labs drawn within the last 3 months of signing the consent form that provide results required of the study may be used in place of screening labs to determine eligibility.

- **Study Visits:** Following screening, this study involves three main study visits (**Figure**).
  - **Visit A:** to establish baseline measurements.
  - **Visit B:** 4 weeks +/- 3 days later to assess study outcomes following blinded, randomized, intervention.
  - **Visit C:** 2 weeks +/- 3 days later to assess study outcomes following cinacalcet add-on therapy. Additional safety visits are involved (black diamonds in **Figure**).

- **Study Drug Interventions:** Enrolled subjects will undergo detailed measurements of outcome variables (see detailed outcome variables below) to establish a baseline (**Figure, visit A**). All study visits will be conducted in the morning, following at least 1 hour of monitored supine rest in the Clinical Research Center. Following study visit A, subjects will be randomized to the blinded study drug by the BWH Research Pharmacies. The initial dose of the blinded study drug will be dictated by the subject's blood pressure and the PI's clinical judgment as it relates to reasonable safety. Subjects with blood pressures near the lower range of our safety margin of 105/50 mmHg will receive the lowest dose, and subjects with higher blood pressures (or known hypertension) will receive a higher dose. The initial doses will range from: eplerenone (EPL) 12.5 mg/d to 25 mg/BID, amiloride 1.25 mg/d to 2.5 mg/BID, or placebo. The EPL arm represents the active intervention: a direct MR antagonist. The placebo arm represents a negative control. Since EPL is expected to influence more than just PTH (EPL will also decrease blood pressure and urinary excretion of potassium and calcium) when compared to placebo, the amiloride intervention represents a *second control* to provide insights into the *mechanism* by which EPL may influence PTH. Like EPL, amiloride is a potassium-sparing diuretic, with mild anti-hypertensive and hypocalciuric effects, and will therefore induce similar changes in blood pressure and urinary potassium/calcium excretion. Unlike EPL, amiloride does not directly block the MR. Rather, it blocks epithelial sodium transport channels (ENaC) in the renal distal tubule (and vascular epithelium).

Following a safety visit at t=2 weeks +/-3 days (see details of safety visits below), the blinded study drug may increase from the initial dose if the PI perceives the risk for hypotension to be low and as long as all safety parameters are fulfilled. The maximum dose any subject may receive is (EPL 50mg BID, amiloride 5 mg BID, placebo 1 dose BID). If the safety parameters are not within normal limits, the safety check will be repeated within 5 days and the dose may be reduced. At t=4 weeks +/- 3 days, subjects will return to the Clinical Research Center to assess outcome variables (**Figure, visit B**). Following visit B, all subjects will receive open-label cinacalcet **in addition** to continuing their blinded study drug. The initial dose of cinacalcet will be dictated by the subject's serum calcium levels and the PI's clinical judgment as it relates to reasonable safety. The initial doses of cinacalcet will range from 15 mg/d to 15 mg BID. Generally, if the subject is hypercalcemic, the initial dose will be 15mg BID, and if they are normocalcemic the dose will be 15 mg/d; however, the PI may alter this if other clinical factors indicate a more judicious approach for safety (i.e. preventing hypocalcemia). Following another safety visit 1 week +/- 3 days after cinacalcet initiation, cinacalcet may be increased to a maximum dose of 30 mg BID. If the serum calcium levels have normalized to within reference

range, it will be at the PI's discretion to increase the dose of cinacalcet, or maintain the same dose, based on the perceived risk of hypocalcemia. If the safety parameters are not within normal limits, the safety check will be repeated within 5 days and the cinacalcet dose may be reduced. Cinacalcet acts as a calcimimetic by allosteric activation of the calcium-sensing receptor and thereby decreases PTH. Cinacalcet administration to subjects with P-HPT will lower PTH and calcium, and will serve to evaluate whether the combination of EPL+cinacalcet can induce additive or synergistic reductions in PTH, when compared to those induced by placebo+cinacalcet (see *Anticipated Results*). Subjects who are instructed to increase their dose following the safety check will be told to take the blinded study drug and cinacalcet everyday at 8AM and 8PM. Subjects will return after 2 weeks +/- 3 days of cinacalcet therapy for the final study visit (**Figure, visit C**).

- *Outcome assessment:* The following measurements will be obtained while fasting at every study visit (**A, B, C**): serum PTH, iCa and total serum calcium, serum phosphate and fibroblast growth factor-23 (FGF-23), 25(OH)D, markers of bone resorption (serum C-telopeptide, urinary N-telopeptide, tartrate-resistant acid phosphatase 5b), markers of bone formation (osteocalcin, bone-specific alkaline phosphatase, P1NP), basic metabolic panel with creatinine, plasma renin activity, serum angiotensin II and ALDO. In addition, 24h urine collections at every study visit, as described above, will be used to measure urinary sodium, potassium, calcium, magnesium, and aldosterone.

Measures of PTH and calcium will be obtained in a standardized fashion after at least 1h of supine rest, at 1h of supine rest, 2h of supine rest, and 3h of supine rest. Subjects will have the option of receiving separate venipunctures at each hour or having an IV placed in their arm for the duration of the study visit which will be used to draw aliquots every hour. The lowest PTH value will be used in analyses.

At study visit A, peripheral blood will be collected for DNA isolation. Although no genetic studies are planned at this time, this DNA will be stored to test future research hypotheses.

Parathyroid tissue will be collected from any subjects that undergo parathyroidectomy (for clinical indications determined by their providers) in the 5 years following their study completion. It is estimated that ~50% of participating subjects may have a surgical parathyroidectomy in the 5 years following their study completion. If the surgery occurs at BWH or MGH, tissue will be collected and flash frozen in liquid nitrogen in the operating room and stored in the BWH pathology

repository, and also formalin fixed in paraffin. Samples will be analyzed for mRNA and protein expression of MR to determine whether there is a correlation of eplerenone-induced  $\Delta$ PTH with MR expression from adenomatous/ hyperplastic parathyroid glands of subjects that undergo parathyroidectomy following study completion. If the surgery occurs at a non-Partners institution, formalin fixed paraffin embedded blocks of tissue will be requested to core a sample and return the block.

Risks will be minimized in this study by using sound inclusion and exclusion criteria that will permit a study population at very low risk of adverse events; use of study interventions that are relatively very low risk; and a very detailed and meticulous monitoring plan. The risk with the highest potential of developing involves that related to study medications, including cinacalcet, eplerenone, and amiloride. These potential side effects are uncommon, but mainly involve laboratory abnormalities that can be monitored. All subjects will have frequent blood tests during the course of the study to ensure safety. Detailed algorithms to manage these risks are also described in the rare case they may occur (below).

